4.1 Inclusion Criteria

Participants must meet all of the following inclusion criteria in order to participate in this study:

- Participated in the original KEEPS trial
- able to understand study procedures
- willing to sign an authorization of consent in order to participate in this study.

4.1 Exclusion Criteria

Exclusion Criteria for MRI and PET imaging:

 Women who have contraindications to MRI or PET for safety reasons, such as an MRIincompatible implant or claustrophobia.

.

4.2 Study Enrollment Procedures

Once IRB approval has been obtained, a standard IRB approved recruitment and informed consent process will be followed. A sample of 118 women who participated in the KEEPS study at Mayo Clinic who meet the inclusion criteria will be considered eligible for the study. Investigators will provide names and contact information for all 118 women who previously participated in the KEEPS study. Participant names, contact information will be recorded directly into the Medidata Rave TM database (described below) on a secure institutional server at the Mayo Clinic. This server will be accessible only to study staff. A study coordinator will send eligible participants a letter by mail and invite them to participate.

Eligible participants will be asked to call the study coordinator if interested, or to mail a response card indicating no interest in further contact. For interested individuals, the study coordinator will provide a detailed description of what the study involves and will collect information on current use of medication and interim cardiovascular, cerebrovascular, or neurologic disease events. Individuals who meet eligibility criteria will scheduled for a study visit at the Mayo Clinic Clinical Research Unit (CRU) of the Center for Translational Science Activities. Participants will be instructed to fast for 12 hours prior to that visit.

A similar procedure will be followed at the participating sites that will obtain their own IRB approvals to enroll participants.

5. STUDY PROCEDURES

6.1 Schedule of Evaluations

Study participants will be scheduled to complete the following assessments and tests over 3-4 visits:

Medical history will include reproductive history (including pregnancy related disorders such as gestational diabetes or hypertensive disorders), cardiovascular and cerebrovascular symptoms or conditions, and use of medications including mHTs (about 30 min).

Clinical examination will include blood pressure, pulse, height, weight, and waist-hip measurement and examination for the diagnosis of MCI according to the National Institute on Aging-Alzheimer's Association (NIA-AA) criteria, ⁹⁶ or dementia according to DSM V. (about 30 min)

Blood will be collected for testing of the lipids, fasting glucose, Vitamin B12 and TSH levels, C-reactive protein, COVID-19 Antibodies, DNA and future testing. Kits will be shipped to the sites and sites will ship all of the samples back to Mayo Clinic in batches (about 30 min).

Questionnaires, assessing menopausal symptoms (Menopause Rating Scale - MRS), and quality-of-life (Utian Quality of Life Scale – UQOL) will be administered. Sleep quality will be assessed using the Pittsburg Sleep Quality Index (PSQI) Profile of Mood States (POMS), . Data will be electronically transferred to UW (about 1 hour).

Neurocognitive testing, including Modified Mini-Mental State Exam, California Verbal Learning Test-II, New York University paragraph recall tests, Benton Visual Retention Test, Subtests from the Wechsler Memory Scale-III (Digit Span and Letter Number Sequencing subtests), Stroop Color Word Test, Trail Making Test A & B, Digit Symbol Coding from the Wechsler Adult Intelligence Scale – 3,, Letter Fluency and Category Fluency tests, Memory Function Questionnaire, Brief Patient Health Questionnaire (about 2 hours)

Brain MRI (about 1 hour)

Brain PET CT (two exams about 2 hours each)

6.2 Description of Evaluations

6.2.1 Screening Evaluation and Consent

Informed consent: Women meeting eligibility criteria by phone screen will be scheduled to report to the Clinical Research Unit (CRU) located at the Charlton Building. The study coordinator will obtain informed consent by Mail in Consent or in person.

6.2.2 Enrollment &Baseline

Initial enrollment visit: After obtaining informed consent, a basic health assessment will be obtained through interview by the study coordinator, including cardiovascular and cerebrovascular symptoms or conditions, menopausal symptoms, and use of medications. Physical measurements will be obtained by CRU staff, including blood pressure, pulse, height, weight, and waist-hip circumference, and a fasting venous blood sample (about 5 tablespoons) will be collected for analysis of lipid panel, fasting glucose, Vitamin B12 and TSH levels, C-reactive protein, DNA and future testing. . with interpretation at the CRU will be obtained. Questionnaires will be administered. The entire visit will take approximately 2 hours.

Baseline Assessments: This is a follow-up study; single tests will be performed.

6.2.3 Follow-up Visits

Visits 2 -4 will include neuropsychological testing, brain MRI and brain PET CT.

Neuropsychological Testing: A comprehensive battery of standardized neuropsychological tests will be administered by an individual trained by personnel overseeing the cognitive Aim (Primary Objective 2) from the University of Wisconsin, Madison, (PI, [name]). The neuropsychological tests are administered in the Research Psychometrics Resource at Mayo Clinic's Center for Translational Science Activities (CTSA) under the direction of [name].

The battery will consist of tests used in the original KEEPS study.(81). In addition to one global measure (Modified Mini-Mental test), all tests have been shown to load on one of four factors derived from data reduction procedures described previously.(82)

The four domains of cognitive performance will include:

- Verbal Learning & Memory function using a composite domain z-score from California Verbal Learning Test (CVLT) and New York University (NYU) Paragraph tests
- 2. Auditory Attention & Working Memory function using a composite domain z-score

- from Wechsler Memory Scale-III Letter-Number Sequencing and Digit Span subtests
- 3. Visual Attention & Perceptual Speed using a composite domain z-score from
- 4. Benton Visual Retention Test, Trail Making Test parts A and B, Stroop, and Digit Symbol Coding tests.
- Speeded Language & Mental Flexibility using a composite domain z-score from Letter (FAS) Fluency and Category (Animals, Fruits, Vegetables) Fluency tests.

Brain MRI: This test will be obtained at the Radiology Department imaging facilities at the Charlton North Building. All MRI studies will be performed on a single 3T system (MAGNETOM, Siemens). A second 3T system with similar hardware and software will be identified as a back-up scanner All MRI sequences used for this study will be acquired in a single sitting with an exam time under 45 min. The operating conditions of the scanner are controlled by its software, and will be in strict adherence to the non-significant risk guidelines as determined by the IRB and as defined by the FDA. The entire system is operated by commercially-available, 510(k) cleared software.

Brain PET Imaging: This test will be obtained at the Radiology Department imaging facilities at the Charlton Building.

F-18 Florbetapir PET: After a 50-minute uptake period, the patient will be positioned on the scanner bed with instructions to remain motionless. Each participant will be injected with 10 mCi of ¹⁸F-Florbetapir (target dose 370 MBq, range 296 - 444 MBq). A helical CT image will be obtained at 50 minutes after injection of ¹⁸F-Florbetapir, followed by a 20-minute PET acquisition consisting of four 5-minute dynamic frames.

F-18 AV-1451 PET: Under a Material Transfer Agreement (MTA) with Avid Radiopharmaceuticals, we have received their AV-1451 radiosynthesis method. We have replicated that method in our PET radiochemistry laboratory to produce AV-1451. We have acquired the regulatory permissions (IND124447; [name] MD) and IRB approval. Participants will receive an intravenous bolus injection of approximately 370 MBq (10 mCi) of ¹⁸F- AV-1451. PET/CT image acquisition will include a low dose CT and then a 20-minute PET acquisition starting at 50-60 minutes after injection of ¹⁸F-T807 and will be performed as 4, 5-minute frames that will then be summed into one static frame. Serial frames will allow for adjustment in the case of patient motion.

6. SAFETY ASSESSMENTS

Participation in this study may involve some discomforts or risks:

Blood Draws: The problems associated with blood drawing include discomfort from insertion of the needle (common), fainting at or about the time of blood drawing (infrequent), bruising at the site of the blood drawing (infrequent), and a clot or infection at the same site (rare).

Cognitive testing: It is possible that anxiety may result from the neuropsychological testing.

Brain MRI: Individuals with claustrophobia may feel too confined and may not tolerate MRI scanning. If this occurs, the MRI scan will be stopped. Individuals will wear earplugs during the scan to reduce the discomfort from noise by the MRI machine.

PET/CT scan: During PET imaging, participants will be exposed to radiation from x-rays and radioactive materials. The amount of radiation exposure has a low risk of harmful effects.

PET compound: The radioactive mixture will be injected in the study participant's vein (intravenous). This can result in a risk of pain or bruising or infection at the site of the needle stick.

¹⁸F-Florbetapir is an agent with specific high affinity for aggregated amyloid similar to other

Thioflavin-T analogs and is non-toxic. This compound is cleared from the body within minutes and no toxic effects have been recorded with doses used in the study. As with any medication, allergic reactions are a possibility.

¹⁸F-T807 (or AV-1451, the AVID Radiopharmaceuticals trade name on the FDA IND) drug safety studies have been completed in rats, mice, dogs and non-human primates, and are available in the Investigator's Brochure on File with the FDA. Testing for binding to CNS relevant receptors, potassium channels, metabolism of ¹⁸F-T807 in mice, effect on human microsomes and hepatocytes, genetic toxicity, and cytotoxicity in normal and cancer cell lines has been performed.

With respect to neurological assessment, the no observed effect level (NOEL) of 18 F-T807 in rats is at least 200 µg/kg (100x MHD, allometrically scaled), the highest dose tested. Thus, 18 F-T807 is not expected to induce CNS effects in humans. With respect to respiratory function, the no observed effect level (NOEL) of 18 F-T807 in rats is at least 200 µg/kg (100x MHD, allometrically scaled), the highest dose tested. In conclusion, no respiratory effects are expected in humans from 18 F-T807. With respect to cardiac function, the NOEL for males and NOEL for females was determined to be 100x MHD (allometrically scaled) on Day 1 and 50x MHD (allometrically scaled) on Day 29. In summary, 18 F-T807 is not expected to prolong the QT interval or have any untoward cardiovascular effects at the intended clinical dose. 18 F-T807 showed the potential for genotoxicity in *in vitro* bacterial reverse mutation assay (Ames test) and chromosomal aberration assays. However, when potential *in vivo* genotoxicity of 18 F-T807 was evaluated in a rat micronucleus study, 18 F-T807 did not increase the number of micronucleated polychromatic erythrocytes at the highest achievable dose level (1600 µg/kg/day for two days). This dose is greater than 750x the intended MHD, and there is no evidence for risk to human subjects at the proposed micro dose.

In summary, single-dose toxicology studies at doses up to 150x MHD and repeat-dose studies up to 50x MHD for one month showed no clinically important effects. ¹⁸F-T807was positive in the *in vitro* hERG assay; however, *in vivo* cardiovascular assessments in dogs showed no evidence of QT prolongation. Nonetheless, until sufficient human cardiovascular safety data are available, initial clinical studies will exclude subjects with a history of risk factors for Torsades de Pointes and subjects taking drugs known to prolong the QT interval. Update: Per FDA update May 2020, recent data shows this is no longer a concern as a risk to participants who have a history of risk factors for Torsades de Pointes and subjects taking drugs known to prolong the QT interval.

Human studies of ¹⁸F-T807 at Mayo Clinic will be performed under FDA Investigational New Drug (IND) approval. ¹⁸F-T807 will be produced for patient use at Mayo Clinic for this study according to cGMP guidelines. We will cross-file our IND submission with the IND approval on file with the FDA as submitted previously by AVID Radiopharmaceuticals (by permission of AVID Radiopharmaceuticals). All studies will also be performed under Mayo Clinic IRB approval and with informed consent for each subject. All subject data will be kept confidential and subjects will be assigned a unique study number known to the study staff to protect their identity as specified by Mayo Clinic IRB guidelines.

Adverse Events: Treatment emergent adverse events were reported in a total of 3 subjects who received a dose of ¹⁸F-T807. Two subjects reported headache, and one subject reported diarrhea. All events were mild in severity and not considered related to ¹⁸F-T807 administration by the investigator. No serious adverse events were reported for any subject receiving ¹⁸F-T807. No consistent or clinically significant changes in vital signs, laboratory values, or ECG results were observed in a completed analysis of 11 subjects.

Radiation Dosimetry: Preliminary radiation dosimetry assessment was performed in three dosimetry subjects. The radiotracer biodistribution among the subjects was consistent and showed rapid hepatobiliary clearance. There were three organs that received estimated doses higher than 0.05

mSv/MBq. The organ that received the largest estimated dose was the upper large intestinal wall $(0.107 \pm 0.009 \text{ mSv/MBq})$, followed by the small intestine and the liver. The Effective Dose was $0.0248 \pm 0.0011 \text{ mSv/MBq}$. This results in an estimated Effective Dose of 9.18 mSv for an anticipated 370 MBq (10 mCi) injection and is comparable to the effective dose of approved ¹⁸F-labeled compounds such as fluorodeoxyglucose (FDG) and florbetapir F 18 injection, and consistent with the primate dosimetry studies.

All participants will receive full supportive care while participating in the protocol. Mayo Clinic physicians remain on-call 24 hours per day to respond to any questions regarding subjects health concerns while participating in this protocol.

Participants may choose to discontinue participation in the study at any time.

7.1 Specification of Study Parameters

Unexpected abnormal results on any testing completed as part of participation in this study will be reviewed by the principal investigator team and reported to the participant in a timely manner depending on the urgency and clinical significance of the abnormality.

7.2 Methods and Timing for Assessing, Recording, and Analyzing Safety Parameters

The Principal Investigator or designee will review all reported side effects up to 8 weeks after the patient's study to assess adverse events. Any adverse event reported to either the principal investigator or his designated research associates by the subject or medical staff caring for the subject will be recorded and the nature and attribution of cause of the event will be discussed. Any new adverse event that is also attributable to the study will be documented as such.

7.3 Adverse Events and Serious Adverse Events

An adverse event includes both, an expected side effect that is of a serious nature, or an unexpected side effect/event regardless of severity. Any new, serious adverse events as described by Common Terminology Criteria for Adverse Events (CTCAE) v3.0 as found at http://ctep.cancer.gov/forms/CTCAEv3.pdf) that are described will be reported to the IRB within 24 hours and the trial will be suspended immediately for review by the IRB. No serious side effects from the research imaging methods in this protocol are conceivable or expected.

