7.4 Reporting Procedures

Any adverse event that is so determined, or reported otherwise to either the principal investigators or their designated research associates by the subject or medical staff caring for the subject and which meets the criteria for a new adverse event that is also attributable to the study will be documented as such.

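### The adverse-event definition leaves out expected, non-serious events, so their recording is not required, and the rules on attribution, IRB reporting and suspension disagree across sections

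*Combined protocol and SAP*

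**What the plan says.** Section 7.3 defines the term: "An adverse event includes both, an expected side effect that is of a serious nature, or an unexpected side effect/event regardless of severity". It then requires new serious events to go to the IRB, with these words on timing and consequence: "that are described will be reported to the IRB within 24 hours and the trial will be suspended immediately for review by the IRB". Its last sentence denies that any serious side effect of the imaging could be conceived of or expected.

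Section 7.2 gives the recording rule. An adverse event reported by the participant or by "medical staff caring for the subject will be recorded and the nature and attribution of cause of the event will be discussed". The next sentence adds: "Any new adverse event that is also attributable to the study will be documented as such". Sections 7.2 and 7.5 also have the investigator review reported side effects for 8 weeks after the participant's study, monthly according to 7.5, in order to assess adverse events. Section 7.6 only refers back to 7.2.

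Section 7.4 mentions documentation for an event "which meets the criteria for a new adverse event that is also attributable to the study will be documented as such". Section 7 (Intervention Discontinuation) speaks of IRB reporting for attributable events only, with suspension left to need.

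Section 6 (Safety Assessments) names the risks: needle discomfort, fainting, bruising, clot or infection from the blood draw; anxiety from cognitive testing; claustrophobia and noise in the MRI; pain, bruising or infection at the tracer injection site; and, in the florbetapir paragraph, "As with any medication, allergic reactions are a possibility".

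**The concern.** The usual order is to record every untoward event and then classify it. Section 7.3 reverses this: seriousness and expectedness decide whether something is an adverse event at all. The risks that section 6 tells us to expect are therefore the ones that drop out when they take their ordinary, non-serious form.

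This matters for two reasons. A low adverse-event count in the final report would partly reflect the definition, and a reader could not tell how much. And non-serious reactions are informative mainly in numbers: several mild reactions at one site or after one tracer batch may point to a procedural or product problem, but only if each one was written down. Florbetapir is given at all sites, with a target enrolment of 492. AV-1451 is given at two sites under an IND.

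The second issue is operational. A coordinator with an event judged unrelated to the study, or a serious event of doubtful cause, finds different instructions depending on which section is opened.

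**Working it through.** There is no stated figure to reproduce and no arithmetic applies. The check is to sort events by the documents' own criteria and then to set the reporting rules side by side.

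**Step 1: the definition.** Section 7.3 does not say against which list expectedness is judged. I assume that a risk named in section 6 is expected. Two levels of expectedness and two of seriousness give four combinations.

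| Event | Inside the 7.3 definition? | Record required by 7.2? |
|---|---|---|
| Unexpected, serious | Yes | Yes |
| Unexpected, non-serious | Yes | Yes |
| Expected, serious | Yes | Yes |
| Expected, non-serious | No | No |

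**Step 2: do other sections close the gap?** Section 7.2 requires a record of adverse events, a term that 7.3 has already narrowed. The 8-week review in 7.2 and 7.5 covers all reported side effects, but its stated purpose is to assess adverse events, so it screens against the same definition; a review is also not a record. Section 7.6 adds nothing of its own. So no section requires an expected, non-serious event to be recorded.

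**Step 3: which named risks fall in the gap?** Needle discomfort (which section 6 calls common), fainting and bruising at the blood draw (both called infrequent), injection-site pain or bruising, anxiety from testing, and a non-serious allergic reaction to florbetapir. A clot, an infection or an allergic reaction that is serious falls inside the definition.

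**Step 4: attribution, IRB reporting and suspension.**

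| Section | Attribution condition | What it requires |
|---|---|---|
| 7.2 | None for recording | Record, then discuss cause; identify attributable events |
| 7.3 | None stated | New serious events to the IRB within 24 hours; immediate suspension |
| 7.4 | Attributable only | Documentation; silent on non-attributable events |
| 7 (Intervention Discontinuation) | Attributable only | IRB report; suspension according to need |

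Two conflicts follow. Sections 7.2 and 7.4 differ on whether a non-attributable event needs documentation, unless 7.4 is read as concerning the label only. Section 7.3 and section 7 (Intervention Discontinuation) differ on whether a new serious event judged unrelated goes to the IRB, and on whether suspension is automatic.

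**Step 5: the closing sentence of 7.3.** Section 6 names infection and allergic reaction after the tracer injection. It does not call them serious, so this is not a direct contradiction. But both can be serious, so a statement that no serious effect is conceivable goes further than section 6 supports.

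**The case against.** Several points on the other side stand.

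- A reader might infer that these risks would never be recorded. The documents do not support that. Serious forms are inside the definition, reported side effects are reviewed for 8 weeks, and the definition is worded as what an adverse event includes, which leaves staff room to record more. The case report forms are not shown, so an adverse-event page may already exist. What can be said is that recording is not required.
- A reader might infer from 7.4 that events judged unrelated are discarded. Section 7.2 answers this: the event "will be recorded and the nature and attribution of cause of the event will be discussed", so recording comes before attribution. The sentence that follows in 7.2, and the similar one in 7.4, can be read as labelling an event attributable. The fair criticism is lack of clarity. Nor does attribution explain the gap for the named risks, since a faint at a blood draw would normally be judged attributable; the definition alone creates it.
- A reader might apply the rule to the AV-1451 events cited in section 6 (two headaches and one diarrhoea) and conclude that none would be captured, then scale this up to a number of lost events. That fails. Section 6 says of them: "All events were mild in severity and not considered related to ¹⁸F-T807 administration by the investigator". Neither headache nor diarrhoea is among its listed procedural and tracer risks, so on the test used here they are unexpected and 7.2 would record them. The denominator for the three subjects is also not given: the 11 subjects belong to the analysis of vital signs, laboratory values and ECG.
- The allergy sentence sits in the florbetapir paragraph. A reaction to AV-1451 may therefore count as unexpected and recordable, so the gap is clearest for florbetapir.
- The study gives no treatment, and no aim, hypothesis or analysis in the statistical section uses adverse-event rates.

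These points limit the consequence. They do not supply a rule that requires expected, non-serious events to be recorded.

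**Conclusion.** The concern holds as a gap in required recording and an inconsistency between sections. One of the four combinations, expected and non-serious, is outside the definition in 7.3, and the ordinary forms of most risks named in section 6 belong to it. Their frequency, or a cluster at one site, could not be reported reliably. The number of events affected cannot be estimated from the documents. Separately, 7.2, 7.3, 7.4 and section 7 (Intervention Discontinuation) do not state one rule for non-attributable events, IRB reporting and suspension.

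This rests on two assumptions: that a risk named in section 6 counts as expected, and that forms or site instructions not shown here do not already require fuller recording. The point concerns the quality of safety data; no planned result for the three aims changes. It is worth correcting because the correction is cheap.

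**What to change.** 1. In 7.3, define an adverse event as any untoward event from the first study procedure to the end of the existing 8-week review, whether or not expected, serious or attributable.
2. In 7.2, require all of these to be recorded, and then classify each by seriousness, expectedness and attribution. Name the list against which expectedness is judged. Use the three classes only to decide onward reporting.
3. Reconcile 7.2, 7.3, 7.4 and section 7 (Intervention Discontinuation) so that one rule covers documentation of non-attributable events, reporting to the IRB, and suspension. Which suspension rule should apply is for the sponsor and the IRB to settle.
4. Reword the closing sentence of 7.3 so that it no longer says serious effects of the imaging are inconceivable, and so that it agrees with the risks in section 6.

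The cost is protocol wording, a short adverse-event page in the electronic case report form if none exists, and more minor entries (bruises, faints) for coordinators. Sample size, procedures and planned analyses do not change.
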